Artificial Intelligence validation trial for polyp detection: Pilot study

Date: 30-10-2019

Study number: s59405

AI validation study for polyp detection

DO NOT USE A ZOOM CAP DURING THE COLONOSCOPY

Any brand of endoscope can be used since we aim to develop a general system, independent of the brand or type.

A GPU computer is connected to the Panasonic AG-MDR25P recorder. This recorder is directly connected via SDI to one of the SDI output ports of the processor. The computer will then in real-time analyse the video that is provided by the processor and show the polyp detections by overlaying a green bounding box on a separate screen.

The endoscopist will perform his colonoscopy as always and he will only see the unaltered video feed from the endoscope processor. In the same room, a second human observer (who is experienced with the appearance of endoscopic video and polyps) will observe the second AI-enhanced screen connected to the computer. The procedure will then go as follows:

1. Start recording with the Panasonic recorder from insertion of the endoscope.
2. Take a still image when starting pullback from the caecum (to mark this point for easier analysis later). The second observer notes down the time indicated on the screen.
3. After the caecum has been reached, the second observer will take note of the following events during the rest of the procedure (by marking it in the attached document):

i. **OBVIOUS FALSE POSITIVES**

The AI system gives a positive prediction but it is an obvious false positive (e.g. stool, biopsy forceps, coagulation tip, diverticulum, air bubble, ...). These are nuisances caused by the system, but would never cause the endoscopist to take action. These detections are **NOT communicated** to the endoscopist.

ii. **OTHER FALSE POSITIVES**

The AI system gives a positive prediction but the endoscopist does not indicate the presence of a polyp. In this case, a polyp could potentially be missed. If this location disappears from the field-of-view of the endoscopist (i.e. out of the image), the second observer should notify the endoscopist and ask him/her to go back and inspect the location in question. Three outcomes are possible here:

1. The location did not contain a polyp, so it was really a false positive.
2. The location did contain a polyp, so it was an additional detection polyp by the system.
3. The location could not be re-identified

iii. **FALSE NEGATIVES**

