A polyp was found by the endoscopist, but the AI system never identified this location to contain a polyp.

iv. **TRUE POSITIVES**

The AI system and the endoscopist found the same polyp (irrespective of who

was first).

4. At the same time, the endoscopist performs the procedure as he would typically proceed until he gets interrupted by the second observer. He then tries to find the location as instructed by the second observer and proceeds after the location has been confirmed to contain a polyp or not.
5. Stop recording when the whole procedure is over.

Additional information needed:

Please provide each video with the following information:

- Number of polyps present in the video
- For each polyp (in the order of appearance or by time indication of when they appeared)
 - o Histological report conclusion
 - o Size
 - o Polypectomy type
 - o Location
 - o Morphology
- Brand and type of endoscope that were used

Statistical analysis plan:

Pilot trial to determine:

- a) Performance of novel Artificial intelligence tool
- b) Power and sample size calculation for ideal set-up of large multicentre validation trial

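### Whether the AI hit or missed an endoscopist-found polyp rests on one observer's live marks, with no stored AI output or verification step specified

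*Combined protocol and SAP*

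**What the plan says.** All references are to the combined protocol and SAP.

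- **Wiring (equipment paragraph).** "This recorder is directly connected via SDI to one of the SDI output ports of the processor". The GPU computer is connected to that recorder, and its task is to "show the polyp detections by overlaying a green bounding box on a separate screen".
- **Who scores (equipment paragraph and step 3).** A second observer "will observe the second AI-enhanced screen connected to the computer". Once the caecum is reached, "the second observer will take note of the following events during the rest of the procedure (by marking it in the attached document"). That form is not part of the text available.
- **False negative (step 3.iii).** An endoscopist-found polyp for which "the AI system never identified this location to contain a polyp".
- **True positive (step 3.iv).** Both found the same polyp, in either order.
- **The observer's other duties (steps 3.i, 3.ii and 4).** The observer separates obvious from other false positives, judges when a flagged site has left the image, and alerts the endoscopist. In step 4 the endoscopist goes back: "He then tries to find the location as instructed by the second observer".
- **Recording (steps 1, 2 and 5).** The recorder runs from insertion to the end of the procedure. The start of pullback is marked with a still image to help later analysis. Each video comes with its polyps listed by order or time, with location.
- **Use (statistical analysis plan, items a and b).** The pilot is to give the tool's performance and the power and sample size for a larger multicentre trial.

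**The concern.** Class iii requires a negative to be established over the whole time a site was in view: the AI did not box it at any moment. Because class iv ignores order, a single brief box decides between iii and iv. The observer may learn that a site matters only when the endoscopist acts on it, and must then rely on having noticed, or on remembering, an earlier box. Meanwhile the same person is writing on the form and directing re-inspections, so lapses in watching are foreseeable, above all in procedures with many flags or polyps.

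The classes are defined by what the AI did, but the data record what one person saw. The sensitivity reported under item (a) would then mix the algorithm with the observer's vigilance, and it would carry over into the sample size under item (b). With no AI output stored, the two components could not be separated from the planned data.

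**Working it through.** **Plan's own figure.** None. The documents state no sensitivity, sample size, alpha, power or observer error rate, so there is nothing to reproduce.

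**Step 1: what the evidence for class iii or iv consists of.** The signal runs from processor to recorder to computer to second screen. The boxes are added at the computer, after the recorder. The recording as described is therefore video without boxes. This is inferred from the wiring; the text does not say it outright. No screen capture, detection log, second reader or adjudication is mentioned. The live mark is the only described evidence of what the AI displayed.

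**Step 2: effect of missed boxes.** Let *s* be the true share of endoscopist-found polyps that the AI boxed, and *m* the share of those boxed polyps for which the observer saw no box. Both are assumptions.

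Apparent sensitivity = s × (1 − m)

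Take 100 endoscopist-found polyps with s = 0.95, so 5 true false negatives:

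- m = 2%: 0.95 × 0.98 = 93.1%; false negatives 6.9, or 1.4 times the true 5
- m = 5%: 0.95 × 0.95 = 90.25%; false negatives 9.75, or 1.95 times
- m = 10%: 0.95 × 0.90 = 85.5%; false negatives 14.5, or 2.9 times

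Apparent sensitivity (%) over a wider range:

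| True s | m = 1% | m = 2% | m = 5% | m = 10% |
|---|---|---|---|---|
| 85% | 84.15 | 83.30 | 80.75 | 76.50 |
| 90% | 89.10 | 88.20 | 85.50 | 81.00 |
| 95% | 94.05 | 93.10 | 90.25 | 85.50 |
| 98% | 97.02 | 96.04 | 93.10 | 88.20 |

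The loss is s × m: from 0.85 points (0.85 × 1%) to 9.8 points (0.98 × 10%).

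**Step 3: effect of wrongly recalled boxes.** Let *r* be the share of truly unboxed polyps that the observer credits to the AI.

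Apparent sensitivity = s × (1 − m) + (1 − s) × r

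The two errors cancel when r = s × m / (1 − s):

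- s = 0.95, m = 5%: r = 0.0475 / 0.05 = 95%
- s = 0.85, m = 5%: r = 0.0425 / 0.15 = 28%
- s = 0.85, m = 1%: r = 0.0085 / 0.15 = 5.7%

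When true sensitivity is high, missed boxes dominate unless wrong recall is very common. When sensitivity is lower and misses are rare, a modest rate of wrong recall reverses the sign.

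**Step 4: carry-over to item (b).** Suppose, as an assumption, that the larger trial is sized for a 95% interval of ±5 points on per-polyp sensitivity, with polyps treated as independent: n = 1.96² × p(1 − p) / 0.05².

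- p = 0.95: 3.8415 × 0.0475 / 0.0025 = 73 polyps
- p = 0.9025 (m = 5%): 3.8415 × 0.0880 / 0.0025, rounded up, = 136 polyps

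**The case against.** The strongest reply has four parts.

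1. **The calls can be checked later.** A reader might infer that a wrong class iii mark is beyond repair. The documents do not support that. The AI's input video is recorded in full, polyps are indexed by order or time, and later analysis is foreseen, so the AI could be run again on the recording. This stands. It is only a partial answer, because the plan specifies no such step and does not say that the software version is fixed or that a re-run would match the live output.

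2. **The direction is not fixed.** A reader might infer that the error can only lower sensitivity. That holds for missed boxes. Memory can also supply a box that was never shown, or one that lay on a neighbouring structure. This stands, and step 3 of the working allows for it.

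3. **Exposure may be small.** A box seen after the endoscopist's find also counts, and a polyp being removed probably stays in view while the observer is alert to it. A wrong class iii mark requires missing every box on that polyp. This stands as a reason why *m* could be low. The documents do not establish that the observer looks away, only that the other duties make it likely. The marking form is not available and might add detail, and nothing states that the computer keeps no output.

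4. **The AI reaches the endoscopist only through the observer, so scoring what the observer sees is legitimate.** That is fair for the arrangement as tested. But step 3.iii is worded by what the AI did, and item (a) asks for the tool's performance.

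**Conclusion.** The point holds as a gap in verification. Classes iii and iv are defined by AI output, scored from one busy observer's live marks, and left without a specified log or check. The size is unknown, because the documents give no observer error rate. On assumed inputs, 95% true recognition with 5% of boxed polyps unseen reads as 90.3%, and across the assumed range missed boxes alone cost between 0.85 and 9.8 points. The multiples of the true false-negative count depend on the chosen baseline of 5 per 100 and should not be read as estimates.

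The conclusion rests on two readings: that the recording lacks the boxes, inferred from the wiring, and that the missing form adds no stored AI output. The pilot remains usable, but as planned its false-negative and true-positive counts are unverified. The change is worth making because it is cheap.

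**What to change.** - Have the GPU computer save a time-stamped log of every displayed box, or capture the second screen.
- Settle class iii or iv from that record for **every** endoscopist-found polyp. Checking only those marked false negative could only raise apparent sensitivity.
- Apply it over the period the plan already scores, after the caecum is reached.
- Fix in advance what counts as a detection, such as a minimum box duration, so that a momentary flicker is not credited by default.
- Ask for a time for each polyp. The plan now accepts order of appearance alone, and a log check needs the time.
- Keep the observer's live marks for prompting the endoscopist and for classes i and ii.
- Report how many live class iii and class iv marks the log changed, in each direction.

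The cost is storage and a short log check per polyp by the existing team, on a computer already in the room. No extra reader or procedure is needed, and live prompting is unchanged. One limit remains: a log can show that a box went unnoticed at a site the endoscopist did not call, but it cannot recover the re-inspection that was never prompted.
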